Trendelenburg, abdominal insufflation and time to completion of cystoscopy. A prospective randomized trial.

NCT05786391

Version Date: 02/28/2023

Protocol Title: Trendelenburg, abdominal insufflation and time to completion of cystoscopy. A prospective randomized trial.

Principal investigator: [name] (Gynecology Faculty)

Statistician: [name]

Study coordinator: [name]

Population: 136 female patients undergoing a planned cystoscopy after Minimally

Invasive Gynecological procedure.

Number of sites: Two sites MHH-TMC and LBJ.

Study duration: 2 years

Subject duration: 6 weeks

General Information (PICO)

This is a randomized controlled trial assessing time to completion of cystoscopy in seconds after minimally invasive gynecologic surgery

We seek to compare the efficiency of the cystoscopy with two interventions: after two interventions:

- 1- patient position during the cystoscopy (Trendelenburg (head down) or flat)
- 2- Abdominal insufflation (insufflation versus no insufflation).

Both interventions are used as usual care and depend on surgeon preference without evidence why one would faster at completing the cystoscopy. Also note that these two interventions are performed multiple times during the surgery itself and outside the cystoscopy procedure routinely.

Our main objective is to assess which intervention or combination of interventions is more efficient

Background

latrogenic injury to the genitourinary tract is a rare, but significant cause of morbidity in patients undergoing gynecologic surgery for benign indications.1–3 In 2012, the American Association of Gynecologic Laparoscopists recommended that routine cystoscopy be performed after all laparoscopic hysterectomies, whereas the American College of Obstetricians and Gynecologists limited the endorsement to prolapse and incontinence procedures.4,5 Universal cystoscopy, where all women undergoing hysterectomy undergo cystoscopy, has been advocated because as many as 75% of genitourinary injuries occur in women without identifiable risk factors.

#UTHealth Houston IRB NUMBER: HSC-MS-22-1081 IRB APPROVAL DATE: 02/28/2023 In one large study, cystoscopy was associated with a median increase in operative time of 17 minutes⁶. Increases in operative time and cost are the most commonly cited concerns regarding cystoscopy with recent estimates of operating room time, not including surgeon and anesthesiologist fees, at \$37 per minute,⁷ cystoscopy results in an additional \$629 per hysterectomy in operating room time alone.

When performing gynecologic laparoscopy, the patient is in a Trendelenburg position (Head down) and the abdomen is normally insufflated to 15 mm Hg during the entire surgery that can take up to 4 hours.

Cystoscopy is done at the end to assure integrity of the bladder and ureteral function, Some surgeons like to do it with the patient in the Trendelenburg position and others flatten the patient position or insufflate the abdomen with the thought that it may reduce the time needed to complete the cystoscopy.

Theoretically, one would predict that performing the cystoscopy under low intraabdominal pressure (no CO2 insufflation) and flat (with the added effect of gravity), would save time in the operating room.

In addition to those modifiable factors, additional factors may include fluid status (total urinary output during the surgery and fluid given intraoperatively as well as blood loss), duration of the surgery, manipulation of the ureters and the bladder (ureterolysis or bladder mobilization/presence of scar tissue) as well as blood loss overall.

Hypothesis:

Non Trendelenburg or flat position and Non insufflation of the abdomen significantly reduces cystoscopy procedure time after gynecologic laparoscopy.

Objective:

We seek to compare the efficiency of the cystoscopy with two interventions: after two interventions:

- 1- patient position during the cystoscopy (Trendelenburg (head down) or flat)
- 2- Abdominal insufflation (insufflation versus no insufflation).

Population

All patients undergoing minimally invasive gynecologic surgery with planned cystoscopy to evaluate urinary tract injury at two main sites: LBJ and MHH-TMC

Inclusion:

Patient undergoing Planned cystoscopy in the benign gynecology service.

Exclusion:

Pregnancy Known urologic anomaly Unplanned cystoscopy

> #UTHealth Houston IRB NUMBER: HSC-MS-22-1081 IRB APPROVAL DATE: 02/28/2023

Cancer surgery

Urogynecology surgery

Patient with comorbidities including cardiac disease, chronic hypertension, any stage kidney disease (including abnormal creatinine level) and use of diuretics.

Patients undergoing extensive ureterolysis

Blood loss more than 500 mls

Contra-indications to position change and insufflation

Study design:

Prospective randomized controlled study 2X2 bloc randomized based on position status and Patient position as **the two interventions** being evaluated:

- 1. Patient Position: flat versus Trendelenburg
- 2. Insufflation status: Yes versus no insufflation.

Outcomes:

Primary outcome: Time in seconds to satisfactorily complete a cystourethroscopy (visualize the dome, the ureteral jets, the bladder mucosa scan and the urethra).

With additional detail in recording time as follows

T0: Start of cystoscopy

T1: time to see one of the ureteral jets

T2 as the second ureteral jet T3: completion of cystoscopy

Exploratory outcome:

Surgeon satisfaction with the interventions (Likert scale questionnaire): The surgeon completes 6 Likert scale questions:

1- Global satisfaction (I will use this method routinely; it satisfies my requirements for cystoscopy).

Randomization

The randomization scheme is maintained by Redcap electronically at the time of consent.

Patients are randomized to 1 of 4 groups based on position and insufflation status

- 1- Position flat, No insufflation,
- 2- Position Trendelenburg, insufflation to 15 mm Hg
- 3- Position Flat, insufflation
- 4- Position Trendelenburg, No insufflation

Randomization occurs in preOp prior to rolling to the operating room.

Neither the surgeons nor the operating room team are blinded to the study group as it required changing position and insufflation.

Cystoscopy medium is sterile water.

#UTHealth Houston IRB NUMBER: HSC-MS-22-1081 IRB APPROVAL DATE: 02/28/2023 Randomization will be performed by the research team (the research fellow who is part of the research team).

It will be performed via redcap using the permutated block method, with an allocation ratio of 1:1:1:1. Patients are blinded to what group they are randomized to.

If cystoscopy is not completed and additional dye is necessary for visualization (as would normally occur outside the setting of the study), then, subjects will be treated as per routine and receive sodium fluorescein (25 mg intravenous sodium fluorescein (concentration 500 mg in 5 mL).

Time will be recorded by the circulating nurse via a stopwatch.

Study duration:

Study duration will be for 6 weeks to allow to review the chart for postoperative outcomes, see variable list to be collected.

Adverse events:

None anticipated outside the routine procedure of cystoscopy.

Cystoscopy risks include possible urinary tract infection. Participation in the study does not increase the risk, as cystoscopy is planned.

There are no additional risks involved with this study beyond the risks discussed at the time of surgical consent. Both position changes (Trendelenberg) and insufflation are part of the laparoscopic procedure. This means that if a patient has a contra-indication to any intervention, she will not be undergoing the procedure. The cystoscopy portion of the procedure is expected to take minutes, in comparison to the procedure, which will take hours. Risks of insufflation and position changes include hemodynamic and respiratory changes that are closely monitored by the anesthesia and the surgical team. We have included this in the consent form.

Data:

Demographic characteristics are abstracted from chart review by study personnel. Characteristics included age, BMI, parity, race/ethnicity, indication for surgery, and medical history. Intervention and surgical data are collected, including type of surgery, surgical start and stop times, cystoscopy start and stop times, estimated blood loss, and whether furosemide or an intravenous fluid bolus was given to assist with assessment of ureteral jets.

Cystoscopy is performed using a 21F sheath and a 70-degree cystoscope. Per protocol, after determining the 12 o'clock position at the bladder dome via the air bubble, the ureteral jets were visualized until surgeon's confidence in the patency of the ureters was determined. Subsequently, a systematic global survey was performed of the bladder, followed by examination of the urethra as the cystoscope was withdrawn.

There are no anticipated adverse events for the two interventions evaluated, as the patient position and insufflation are two variables that routinely occur during surgery.

#UTHealth Houston IRB NUMBER: HSC-MS-22-1081 IRB APPROVAL DATE: 02/28/2023

At the conclusion of the study (when the final randomized patient met the 6-week postoperative mark), all patient medical records will be reviewed for operative data including operative complications.

Statistical analysis

Continuous variables are described with mean (SD) or median (range) depending on the distribution of the data. Statistical tests for continuous data were based on 1-way analysis of variance for normally distributed data, or the Kruskal-Wallis test for nonnormal data. This is determined by histogram plots and Levene test. Categorical variables are described with numbers (percentages) and compared using the χ^2 test. All statistical tests were 2-tailed, and were based on the intent-to-treat principle.

Sample size analysis

Median and IQR cystoscopy duration is 168 (86-286) seconds⁸, a clinically significant improvement in cystoscopy times would be 108 (69-160).

	Insufflation -	Insufflation +
Flat	Group1	Group2
T-Berg	Group3	Group4

Using analysis of variance, 28 subjects in each arm for a total of 112 subjects would be needed to detect an effect size of > 60 seconds, with 80% power and a 2-tailed alpha of 0.05 to achieve statistical significance using the frequentist method. To account for 20% drop outs, we will include 34 patients in each group for a total of 136 cystoscopy procedures,

The one minute decrease in operative time is used based on prior studies showing that the use of "Lasix" intraoperatively can significantly reduce cystoscopy duration by about 78 seconds.⁸

- CONSORT diagram will be performed
- We will evaluate for the presence of interaction between the different interventions as two interventions are employed at the same time.
- Intention to treat analysis will be performed
- All unadjusted outcomes will be reported descriptively (mean SD/ median IQR)
- For all outcomes, we will conduct intent-to-treat Bayesian analysis to calculate probabilities of intervention benefits and harms. We will use neutral priors and exclude large treatment effects. We will report posterior medians of group differences, their corresponding 95% credible intervals, and probability of treatment benefit.

Funding:

IRB NUMBER: HSC-MS-22-1081
IRB APPROVAL DATE: 02/28/2023

None

OVERSIGHT RESPONSIBILITIES

Oversight of the trial is provided by the Principal Investigator (PI), [name] and Co-investigators Drs [name] and [name].

Ethics

- IRB approval will be sought for this study, and admin Approval sought from Harris Health and MHH approval as well as a departmental review.

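### Item 1 of the surgeon questionnaire puts intended routine use and adequacy of the method under one rating, so discordant views cannot be told apart

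*Combined protocol and SAP*

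**What the plan says.** The Outcomes section of the combined protocol and SAP lists, under "Exploratory outcome", "Surgeon satisfaction with the interventions (Likert scale questionnaire"). It then states: "The surgeon completes 6 Likert scale questions". Only the first question appears in the text: "Global satisfaction (I will use this method routinely; it satisfies my requirements for cystoscopy").

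Three other places bear on how that item will be answered and used.

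- General Information (PICO): "Both interventions are used as usual care and depend on surgeon preference".
- Randomization: patients go to one of four combinations of position and insufflation, and "Neither the surgeons nor the operating room team are blinded to the study group".
- Sample size analysis, closing list: "For all outcomes, we will conduct intent-to-treat Bayesian analysis to calculate probabilities of intervention benefits and harms".

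The documents give no number of response points, no anchors and no scoring rule for the questionnaire. They describe no separate rating for the two statements in item 1.

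**The concern.** As printed, one rating has to answer two questions. The first statement is about what the surgeon will do in later cases. The second is about whether the method met the surgeon's needs. In this trial the two can come apart. Surgeons already have preferences, randomization may give them a combination they would not have chosen, and they know which one they were given. A surgeon who found the assigned combination adequate but will go back to the usual one has no response that says so.

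What is at stake is the interpretation of this item. The planned analysis will attach a probability of benefit to it. If arms differ, the reader cannot tell whether surgeons were more satisfied with one method or only more inclined to keep using it. A single combined answer cannot be taken apart after it has been collected.

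**Working it through.** The documents state no scale, expected score, SD or power for satisfaction, so there is no figure of the plan to reproduce. The check is mainly one of wording.

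**Step 1. Set the outcome beside the item.** The outcome is satisfaction with the interventions. The item's label is global satisfaction, which matches. Its bracketed text has two parts:

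| Part | What it asks | Time it refers to |
|---|---|---|
| First statement | Will the surgeon adopt the method? | Future practice |
| Second statement | Did the method meet the surgeon's requirements? | The method itself |

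**Step 2. Go through the four answer patterns.**

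| Adequate? | Will adopt? | What one rating can convey |
|---|---|---|
| Yes | Yes | High score, readable as overall satisfaction |
| No | No | Low score, readable as overall dissatisfaction |
| Yes | No | No correct single answer; the score depends on how the surgeon weighs the parts |
| No | Yes | The same problem; probably uncommon |

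Two of the four patterns are readable and two are not. The third is plausible here because of the preference statement in General Information and the random assignment. The documents do not say how often it would occur.

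**Step 3. Can a loss of power be put on this?** It is natural to try. The inputs below are assumptions, not figures from the documents, except the group size: 136 randomized in four equal arms gives 2 × 34 = 68 per level of each factor. Assume an approximately continuous score, a two-sided alpha of 0.05, a two-sample t-test, and a factor that shifts adequacy by 0.5 SD. An item on adequacy alone then has power 0.825.

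Suppose surgeons average the two statements, with correlation r between them, and the factor shifts intended use by s SD. The effect on the joint item is

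d = [(0.5 + s)/2] / √[(1 + r)/2].

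| Shift in intended use, s | d for r = 0.3, 0.5, 0.7 | Power at 68 v 68 |
|---|---|---|
| 0 | 0.310, 0.289, 0.271 | 0.435, 0.387, 0.348 |
| 0.25 | 0.465, 0.433, 0.407 | 0.77, 0.71, 0.65 |
| 0.5 | 0.620, 0.577, 0.542 | 0.95, 0.92, 0.88 |

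For example, with s = 0 and r = 0.3, d = 0.25/√0.65 = 0.310. With s = 0.5 and r = 0.3, d = 0.5/√0.65 = 0.620.

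If instead surgeons agree only as far as the weaker statement and s = 0, simulation gives d = 0.235, 0.218 and 0.196, and power of about 0.275, 0.24 and 0.206.

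The joint item thus ranges from much worse than the single item (power 0.21) to better than it (0.95), depending on s, r and the response rule. None of these is in the documents. The group size is also an upper limit: at the 112 subjects the plan needs after dropout (2 × 28 = 56 per level), even the single item has power of about 0.75. The t-test is not the planned analysis either. The arithmetic shows that the effect on power is undetermined.

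**The case against.** The strongest case on the other side has four parts.

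1. **Willingness to reuse a method is a fair facet of satisfaction with it.** This stands. The documents do not limit satisfaction to adequacy in the case just done, and where the two statements agree the rating is a reasonable global score. A reader might infer from the double wording that the item cannot measure satisfaction at all, or that no arm difference on it could ever be read as one. The documents do not support that. Only discordant answers are ambiguous, and their frequency is unknown.

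2. **The instrument is not fully visible.** This also stands, as a limit. Six questions are announced and one is shown. The bracket may explain the label and not be the literal question, and one of the other five may already ask about adequacy or intended use. The missing text cannot be counted as an omission. Even so, the bracket is the only definition of the item given, and it defines one score by two things. If it is a gloss, which of the two is scored still needs to be said.

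3. **A reader might infer that the joint item costs the trial power for satisfaction.** The calculation above does not establish that. The loss appears when intended use is assumed not to move at all, and turns into a gain under averaging when both statements move equally.

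4. **The outcome is exploratory and this is one question of six.** This is correct, and it sets the grade of the point. It is no reason to keep a wording that is easily improved.

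**Conclusion.** The point holds in a limited form. Item 1, as printed, cannot separate satisfaction from intended routine use when a surgeon's views on the two differ, and this trial's setting makes such differences plausible. A low or middle score, or an arm difference on this item, is then ambiguous between the two readings.

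The reach is small: one question of an exploratory questionnaire. The primary outcome of time in seconds, the sample size and the error rates do not depend on it. No size can be given for any loss of power.

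The conclusion rests on two assumptions: that the printed text is the question surgeons answer, or at least defines its score, and that the five questions not shown do not already separate the two parts. It is a cheap improvement, not a flaw in the trial's main comparison.

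**What to change.** Before data collection, split item 1 into two items, each with its own rating:

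- (a) a statement that the method met the surgeon's requirements in this cystoscopy, named as the global satisfaction item;
- (b) the statement on routine use, scored by itself and reported as intended use.

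Do not combine the two scores. If one of the other five questions already asks for (a) or (b), keep that question and only remove the corresponding half from item 1.

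The cost is at most one more questionnaire line and one more REDCap field, a few seconds per case. If neither part is already asked elsewhere, the form has seven questions instead of six. No extra patients, staff or procedures are needed.

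### Do the different arm numbers in the Randomization list and the 2x2 table put the factor effects at risk?

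*Combined protocol and SAP*

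**What the plan says.** The Randomization section states "Patients are randomized to 1 of 4 groups based on position and insufflation status" and then gives a numbered list. Item 1 is flat without insufflation. The others read "2- Position Trendelenburg, insufflation to 15 mm Hg", "3- Position Flat, insufflation" and "4- Position Trendelenburg, No insufflation". The allocation is held in REDCap; the section gives no database code for any arm.

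Under Sample size analysis, a 2x2 table has columns for insufflation absent and present. Its rows read "Flat Group1 Group2" and "T-Berg Group3 Group4". This is the only place where the labels Group1 to Group4 occur.

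The bullets that close that section hold the analyses in which arm identity matters: "We will evaluate for the presence of interaction between the different interventions" and, for the Bayesian analysis, "We will report posterior medians of group differences".

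**The concern.** Two parts of one protocol attach different numbers to three of the four arms, and nothing in the text maps one set to the other. The main objective under General Information is to find out which intervention, or which combination, is more efficient. That answer, the interaction check and the Bayesian group differences all need the right name on each arm. If the allocation were stored as the digits 1 to 4 in list order and the analyst read them with the table, or the reverse, one factor could be credited with the other's effect. The planned four-group test would give no warning, since it ignores which label belongs to which group.

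**Working it through.** The plan gives no figure to reproduce here. The check is a comparison of the two numberings, followed by the contrasts that would result from mixing them.

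**Step 1: the two numberings side by side.**

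| Number | Randomization list | 2x2 table |
|---|---|---|
| 1 | flat, no insufflation | flat, no insufflation |
| 2 | Trendelenburg, insufflation | flat, insufflation |
| 3 | flat, insufflation | Trendelenburg, no insufflation |
| 4 | Trendelenburg, no insufflation | Trendelenburg, insufflation |

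Both columns contain the same four factorial cells. Numbers 2, 3 and 4 differ.

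**Step 2: patients exposed if the two were mixed.** With the planned 34 per arm (136 in total):
- in differently numbered arms: 3 × 34 = 102;
- wrong position label (numbers 2 and 3): 2 × 34 = 68;
- wrong insufflation label (numbers 3 and 4): 2 × 34 = 68.

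**Step 3: effect on the contrasts if the two were mixed.** Write F0, F1, T0, T1 for the true means (flat or Trendelenburg; insufflation 0 = no, 1 = yes).
- Position = (T0 + T1 − F0 − F1)/2
- Insufflation = (F1 + T1 − F0 − T0)/2
- Interaction, as a difference of differences, D = (T1 − T0) − (F1 − F0)

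Stored by the list and read by the table, the cell reported as F1 is really T1, T0 is really F1, and T1 is really T0. Substituting:
- reported position = (F1 + T0 − F0 − T1)/2 = −D/2;
- reported insufflation = (T1 + T0 − F0 − F1)/2 = true position;
- reported interaction = (T0 − F1) − (T1 − F0) = −2 × true insufflation.

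Stored by the table and read by the list, the same steps give reported position = true insufflation, reported insufflation = −D/2, and reported interaction = −2 × true position.

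As an illustration, take a hypothetical position-only effect of 60 s, using the protocol's 108 and 168 s as if they were cell means (F0 = F1 = 108, T0 = T1 = 168). List-to-table mixing reports position (108 + 168 − 108 − 168)/2 = 0, insufflation (168 + 168 − 108 − 108)/2 = 60 s and interaction 0. Table-to-list mixing reports position 0, insufflation 0 and interaction −120 s.

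**Step 4: what the numbering cannot touch.** One-way analysis of variance and Kruskal-Wallis statistics depend on how patients are grouped, not on what the groups are called, so their p-values are the same under either numbering. The sample size and the allocation ratio do not use arm numbers.

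**Step 5: does the plan lead anyone to mix them?**
- The list names position and insufflation for each arm; the table names them in its row and column headings. Neither is ambiguous alone.
- The hypothesis is stated in words, and no outcome or analysis sentence cites an arm by number.
- The protocol uses the same item numbering for ordinary lists, such as the two interventions and the satisfaction question, so the list digits need not be codes at all.
- The table stands between the assumed cystoscopy times and the sample size calculation. It illustrates the factorial layout and is not presented as an analysis key.
- Study design names the two factors and their levels, which is what an analyst needs to fit an interaction.

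**The case for a change.** The best case for a change is that the mismatch is certain, the error would be hard to see, and the repair is cheap. A position effect reported as an insufflation effect would look believable, because the hypothesis expects both factors to matter, and the overall test would not expose it. A research fellow randomizes and a statistician is named separately, so the allocation may change hands. The opening sentence of Study design names position twice and omits insufflation, and the data items listed under Data do not include the position or insufflation actually used.

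The mismatch and the algebra stand. What is missing is a route from the text to the error. It needs bare digits in storage, no value labels with them, and an analyst who decodes with the other section. The protocol describes none of these and gives no basis for a probability. Database codes normally sit in a data dictionary, and the variable list mentioned under Study duration is not in the text available, so it cannot be said that the coding is undocumented. The Study design sentence is followed at once by both factors, correctly named.

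**Conclusion.** The two places do number three of four arms differently; this is a clerical slip. Every arm is defined in words in both, the words agree on the same four cells, and no planned analysis calls on a number. Carried out as written, the plan attributes the position, insufflation and interaction effects correctly. The 102 patients and the shifts of 60 s and 120 s describe a mix-up that is assumed, not one that the plan causes or makes likely. Even then, the overall test would be unchanged, and the hypothesised best arm has number 1 in both places, so the best combination would be misnamed only if another arm proved fastest.

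This rests on the allocation being carried with its arm descriptions, as is usual and as the operating team needs in order to set position and insufflation. Aligning the two numberings would be housekeeping; it would alter no test, estimate or sample size.

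### Allocation is generated in pre-op and not stated to be withheld from the unblinded surgical team until cystoscopy, leaving an avoidable interval in which care could differ by arm

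*Combined protocol and SAP*

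**What the plan says.** The Randomization section of the combined protocol and SAP has two sentences on timing: "The randomization scheme is maintained by Redcap electronically at the time of consent" and "Randomization occurs in preOp prior to rolling to the operating room". On who randomizes, it says "Randomization will be performed by the research team (the research fellow who is part of the research team". On blinding, it says "Neither the surgeons nor the operating room team are blinded to the study group as it required changing position and insufflation". It states that patients are blinded. It does not say when the surgical team learns the arm, or that the arm is held back until cystoscopy.

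The Background places cystoscopy at the end of surgery and describes the abdomen as "insufflated to 15 mm Hg during the entire surgery that can take up to 4 hours". Besides position and insufflation, it says that "additional factors may include fluid status (total urinary output during the surgery and fluid given intraoperatively as well as blood loss", and goes on to duration of surgery and manipulation of the ureters and bladder.

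The Data section collects "type of surgery, surgical start and stop times, cystoscopy start and stop times, estimated blood loss", and whether furosemide or a fluid bolus was given to help see the jets. The Statistical analysis and Sample size analysis sections specify intention-to-treat comparisons, a check for interaction and a Bayesian analysis. They name no covariates.

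**The concern.** The randomized interventions exist only from the start of cystoscopy (T0). Everything between allocation and T0 is ordinary surgery and anaesthesia, and ideally it should not depend on the arm. Here the arm exists before the patient reaches the operating room, and the people who then manage fluids and operate near the ureters are not blinded to it.

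The General Information section says that use of these interventions depends on surgeon preference, and the Hypothesis section favours flat position without insufflation. A team that knows the arm early could, without intending to, prepare the patient differently for a cystoscopy it expects to be slow. The primary time would absorb that difference. Intention-to-treat analysis would not remove it, because patients would still be analysed in the arm assigned. Blinding the patient and having the circulating nurse time with a stopwatch do not address it either, since neither governs what the surgical team does before T0.

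**Working it through.** The plan states no figure for this risk, so there is none to reproduce. The check sets the sections side by side and then illustrates scale.

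**1. Order of events**

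| Step | Source |
|---|---|
| Allocation generated in pre-op by the research fellow through REDCap | Randomization |
| Operation, up to 4 hours | Background |
| T0: start of cystoscopy, when the assigned position and insufflation matter | Outcomes; Randomization |
| T1, T2, T3: first jet, second jet, completion | Outcomes |

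Allocation therefore precedes T0 by the whole operation: up to about 4 hours, plus any wait between pre-op and the start of surgery.

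**2. Does anything need the allocation that early?** The reason given for not blinding the team is that position and insufflation have to be changed. That requires the team to know the arm at cystoscopy. It gives no reason for allocating before the operation.

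**3. Which factors could be steered?** The Background's list is worded as possible factors.
- Discretionary to a degree: fluid given, and use of a diuretic or bolus.
- Discretionary only in part: ureteral or bladder work, much of which the operation dictates.
- Not readily steered: blood loss and scar tissue. Urine output is a result of care, not a decision.

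**4. Would a difference be prevented, seen or adjusted for?**
- Prevented: no text withholds the arm or standardizes these factors across arms.
- Seen: furosemide and bolus use are in the Data section's list, so an imbalance there would be visible. Total fluid, urine output and manipulation are not in that list. However, the list is introduced as inclusive, and the Study duration section refers to a variable list that is not shown, so their absence from the case form is not established.
- Adjusted for: no adjustment is specified. With allocation in pre-op, these measures arise after randomization, so adjusting for them would itself be questionable.

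**5. Scale only.** Inputs from the Sample size analysis section: furosemide shortens cystoscopy by about 78 s, and the target effect is 60 s. Assumed, not in the documents: the difference d between the two levels of a factor in the proportion of patients given such a measure.

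Shift = 78 s × d; share of target = shift / 60 s.

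| d (assumed) | Shift | Share of 60 s |
|---|---|---|
| 0.10 | 78 × 0.10 = 7.8 s | 13% |
| 0.20 | 78 × 0.20 = 15.6 s | 26% |
| 0.25 | 78 × 0.25 = 19.5 s | 33% |

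These rows do not estimate the bias from early allocation. Furosemide or a bolus may be given during cystoscopy, when the team must know the arm whatever the time of allocation. The documents do not say how much use falls before T0.

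**The case against.** The best reply is that the documents do not show the team learning the arm in pre-op. A research fellow randomizes, no time of disclosure is given, and the stated reason for not blinding concerns the cystoscopy step. That stands. A reader might infer that surgeons know the arm for up to 4 hours, but the text supports only that the arm exists by then and is not stated to be withheld.

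Four further objections have force:
- A reader might conclude that differential management could go unseen. The text does not support this: furosemide and bolus use are recorded, and the full variable list is not available.
- A reader might take 8 to 20 s as the size of the bias. The documents do not support this either, because the differences in use are assumed and the 78 s is not tied to use before T0.
- The two timing sentences need not conflict. If consent is taken in pre-op, they agree.
- The exclusions for diuretic use, blood loss over 500 mL and extensive ureterolysis narrow the range over which these factors can vary.

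None of this closes the interval. Allocation still precedes T0 by the whole operation, no step keeps it from an unblinded team, and discretionary care that may affect the outcome takes place in between.

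**Conclusion.** The point holds as a design weakness that is cheap to remove. The plan leaves an interval, as long as the operation, in which the arm exists, is not stated to be withheld, and could influence care before T0. The plausible routes are discretionary fluid or diuretic use and, in part, ureteral or bladder work.

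The documents show that the risk is open. They do not show that surgeons steer care by arm, and they allow no estimate of the resulting bias. What they give on scale is that one jet-assisting measure is credited with 78 s, which exceeds the 60 s target (78 / 60 = 1.3). A modest imbalance before T0 would therefore matter if it occurred. The conclusion assumes that no separate procedure, outside these documents, already withholds the arm until cystoscopy.

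**What to change.** Replace the timing sentences in the Randomization section with one rule: consent and eligibility are completed in pre-op, and the REDCap allocation is generated and opened only when the surgeon declares the operative part finished and is ready for cystoscopy.

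Confirm that total intraoperative fluid, urine output and ureteral or bladder manipulation up to that moment are on the case form, and add any that are missing. Under the new rule they are pre-randomization covariates. Add a prespecified analysis of the primary time adjusted for them to the Statistical analysis section; otherwise the fields would be collected but not used.

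The cost is protocol wording, at most three chart fields, and the need for someone on the existing team with REDCap access to open the allocation at the end of each of the 136 cases at two sites. The study is unfunded, so that availability should be settled beforehand. The sample size calculation is not affected. A side benefit is that blood loss over 500 mL and extensive ureterolysis, both listed as exclusions, would be known before allocation.

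The change does not remove unblinded management during cystoscopy or the unblinded judgement of when it is complete.
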